**Figure 1. Study Design**

### 5.1.1 Screening

At the Screening Visit, subjects who provide written (signed and dated) informed consent prior to any study specific procedures, will receive a unique subject number via the Interactive Response Technology (IRT) system and will undergo the study procedures identified in Section 5.3.1 associated with the Screening Visit. The investigator or designee will evaluate whether the subject meets all of the eligibility criteria specified in Section 5.2.1 and Section 5.2.2 during the period from the Screening Visit through Study Day 1 prior to dosing and record the results of this assessment and the details of the informed consent process in the subject's medical records.

Eligible subjects have up to 42 days following the Screening Visit to enroll into the study.

#### 5.1.1.1 Rescreening

Subjects who meet all eligibility criteria with the exception of up to three exclusionary laboratory parameters may rescreen once within the 42-day screening period without prior AbbVie approval. However, subjects with any of the following exclusionary values will not be allowed to rescreen: exclusionary HCV genotype, a positive hepatitis B surface antigen, positive human immunodeficiency virus (HIV) antibody, or confirmed

pregnancy. Subjects with more than three exclusionary laboratory results will require approval from the AbbVie Study Designated Physician prior to rescreening. Subjects being rescreened because of exclusionary laboratory parameter(s) must have the related panel(s) repeated (e.g., exclusionary ALT requires a repeat chemistry panel) within the same screening period and must meet all eligibility laboratory criteria on any panel that is repeated.

For subjects who do not meet the study eligibility criteria, the site personnel must register the subject as a screen failure in both IRT and electronic data capture (EDC) systems.

### **5.1.2 Treatment Period (TP)**

Subjects who meet the eligibility criteria will be enrolled to either 12 or 24 weeks of combination therapy with or without RBV as described below and [Table 5](#).

HCV GT1-infected subjects who are either treatment-naïve or treatment-experienced will receive ABT-450/r/ABT-267 and ABT-333. Subjects with HCV GT1a infection and all GT1-infected subjects with compensated cirrhosis will receive RBV.

The treatment duration will be 12 weeks for all subjects except HCV GT1a-infected subjects with compensated cirrhosis who will receive treatment for 24 weeks. Treatment duration of 12 weeks for HCV GT1a-infected subjects with compensated cirrhosis may be selected by the investigator where consistent with the approved local label. Subjects will receive study drug regimens according to criteria listed in [Table 5](#).

**Table 5. Treatment Regimen and Duration**

Subject Population	Treatment Regimen*	Treatment Duration
Genotype 1a, without cirrhosis	ABT-450/r/ABT-267 + ABT-333 + ribavirin	12 weeks
Genotype 1a, with cirrhosis	ABT-450/r/ABT-267 + ABT-333 + ribavirin	24 weeks**
Genotype 1b, without cirrhosis	ABT-450/r/ABT-267 + ABT-333	12 weeks
Genotype 1b, with cirrhosis	ABT-450/r/ABT-267 + ABT-333 + ribavirin	12 weeks

\* Follow the genotype 1a dosing recommendations in patients with an unknown genotype 1 subtype or with mixed genotype 1 infection.

\*\* Treatment for 12 weeks may be considered in some patients where consistent with the approved local label.

The site will enter subject's genotype (1b/Non-1b), fibrosis stage and prior IFN-based treatment information in the IRT system in order to assign subject's treatment regimen as described in [Table 5](#).

ABT-450/r/ABT-267, ABT-333 and RBV (if applicable) will be administered as described in [Section 5.5.1](#). Subjects will receive instructions about the study drugs and the dosing schedule at the Day 1 Visit. The study drugs will be dispensed at the visits indicated in [Table 7](#).

All subjects will continue to return to the site on an outpatient basis through Week 12 or Week 24 depending on treatment assignment, following the study procedures identified in [Table 7](#). Subjects could also return to the site as an unscheduled study visit for additional safety visits if the investigator feels it is necessary. Sites should ensure that subjects adhere to the study visits. Sites should provide additional study drug for subjects who cannot complete their study visit per the visit schedule to ensure they do not run out of study drug prior to their next study visit. Compliance is critical to ensure adequate drug exposure.

Some of the Treatment Period study visits and visit activities (including but not limited to vital signs, clinical laboratory tests, and concomitant medication assessment) may be conducted in the home or non-hospital/clinic environment by qualified individuals at the

request of the Investigator, with approval from the Sponsor, and with the agreement of the subject.

Virologic failure criteria will be evaluated and applied by the investigator as detailed in Section 5.4.3.

Subjects who prematurely discontinue from the Treatment Period should return for a Treatment Discontinuation Visit and undergo the study procedures as listed in Table 7 and as described in Section 5.4.1. Ideally, this should occur on the day of study drug discontinuation, but is recommended to be no later than 2 days after their final dose of study drugs and prior to the initiation of any other anti-HCV therapy.

Following completion or premature discontinuation of study drug treatment, all subjects will enter the 260-week Post-Treatment Period. The Treatment Period will assess safety, antiviral response, progression of liver fibrosis, patient reported outcomes and clinical outcomes, including all-cause death, liver-related death, liver decompensation, occurrence of hepatocellular carcinoma, and liver transplantation.

### **5.1.3 Post-Treatment Period (PT)**

All subjects who receive at least one dose of study drugs will be monitored for an additional 260 weeks following the last dose of study drugs. Subjects will return to the study site as outlined in Table 7 for Post-Treatment procedures. The Post-Treatment Period will begin the day after the last dose of study drugs. Subjects could also return to the site as an unscheduled study visit for additional safety visits if the investigator feels it is necessary. Subjects who prematurely discontinue the Post-Treatment Period should return to the site for a Post-Treatment Discontinuation Visit as outlined in Table 7.

The post-treatment period will assess safety, antiviral response, progression of liver fibrosis, patient reported outcomes, and clinical outcomes, including all-cause death, liver-related death, hepatocellular carcinoma, liver decompensation and need for liver transplantation.

Some of the Post-Treatment Period study visits and visit activities (including but not limited to vital signs, clinical laboratory tests, and concomitant medication assessment) may be conducted in the home or non-hospital/clinic environment by qualified individuals at the request of the Investigator, with approval from the Sponsor, and with the agreement of the subject.

## **5.2 Selection of Study Population**

The study population consists of HCV genotype 1-infected adult subjects with or without compensated cirrhosis, who are treatment naïve or IFN-based treatment experienced.

Subjects who meet the inclusion criteria and who do not meet any of the exclusion criteria will be eligible for enrollment into the study.

### **5.2.1 Inclusion Criteria**

1. Male or female at least 18 years of age at time of screening.
2. Female who is:
  - practicing total abstinence from sexual intercourse (minimum 1 complete menstrual cycle)
  - sexually active with female partners only
  - not of childbearing potential, defined as:
    - postmenopausal for at least 2 years prior to screening (defined as amenorrheic for longer than 2 years, age appropriate, and confirmed by a follicle-stimulating hormone (FSH) level indicating a postmenopausal state), or
    - surgically sterile (defined as bilateral tubal ligation, bilateral oophorectomy or hysterectomy) or has a vasectomized partner(s);
  - of childbearing potential and sexually active with male partner(s):
    - currently using at least one effective method of birth control at the time of screening and
    - agree to practice two effective methods of birth control while receiving study drugs (as outlined in the subject information and consent form or

---

other subject information documents), starting with Study Day 1 and for 30 days after stopping study drug, or 7 months after stopping drug if receiving RBV (or as directed by the local RBV label). (Note: Ethinyl estradiol-containing hormonal contraceptives, including oral, injectable, implantable, patch and ring varieties, may not be used during study drug treatment).

3. Males who are not surgically sterile who are sexually active with female partner(s) of childbearing potential must agree to practice two effective forms of birth control (as outlined in the subject information and consent form or other subject information documents) throughout the course of the study, starting with Study Day 1 and for 30 days after stopping study drug, or for 7 months after stopping study drug if receiving RBV (or as directed by the local RBV label).
4. Chronic HCV-infection prior to study enrollment. Chronic HCV-infection is defined as one of the following:
  - Positive for anti-HCV Ab or HCV RNA > 1,000 IU/mL at least 6 months before Screening, and positive for HCV RNA and anti-HCV Ab at the time of Screening; or
  - HCV RNA > 1,000 IU/mL at the time of Screening with a liver biopsy consistent with chronic HCV-infection (or a liver biopsy performed prior to enrollment with evidence of chronic hepatitis C disease).
5. Screening laboratory result indicating HCV genotype 1-infection.
6. Subjects must be able to understand and adhere to the study visit schedule and all other protocol requirements and must voluntarily sign and date an informed consent form, approved by an Institutional Review Board (IRB), prior to the initiation of any screening or study specific procedures.

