### **Pregnancy Test**

Pregnancy tests are not required for female subjects with documented prior bilateral tubal ligation, bilateral oophorectomy or hysterectomy or for subjects who are confirmed to be

postmenopausal. Confirmation of postmenopausal status measured by FSH will be obtained at the Screening Visit only for all female subjects.

For females of childbearing potential:

- A serum pregnancy test will be performed at the Screening Visit only and sent to the central laboratory for analysis.
- Pregnancy testing will be performed as specified in [Table 7](#) regardless of treatment regimen.
- Females of childbearing potential that were treated with DAAs only in the Treatment Period should have urine pregnancy testing done through Post-Treatment Week 4.
- Subjects that receive a RBV containing regimen will have pregnancy tests performed monthly throughout the Treatment Period and for a minimum of 7 months after the discontinuation of RBV, or according to the local RBV label and/or local treatment guidelines for RBV.
- Urine pregnancy testing will be performed on-site during the study visit if there is a scheduled visit. If there is not a scheduled study visit, subjects may either have pregnancy testing performed at the site as an unscheduled study visit using an unscheduled test kit or a urine pregnancy test may be conducted by the subject at home with a pregnancy test kit provided by the site. If a urine pregnancy test is performed at home, site personnel should contact these female study subjects to capture the results of any study-related pregnancy tests in the source records only.
- If a urine pregnancy result is positive a confirmatory hCG serum test should be collected and sent to the central lab.

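### Criterion 2 labels a fertile woman with a vasectomized partner as not of childbearing potential, so a site could omit her between-visit monthly pregnancy tests on and after ribavirin, although no exemption list excuses her (minor)

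*Protocol*

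**What the plan says.** **Definition.** Protocol 5.2.1, criterion 2, sets out who counts as not of childbearing potential. One part is confirmed postmenopausal status. The other is "surgically sterile (defined as bilateral tubal ligation, bilateral oophorectomy or hysterectomy) or has a vasectomized partner(s"). The Synopsis repeats this. Criterion 2 gives separate routes, without that label, to abstinent women and to women "sexually active with female partners only". A further route covers women of childbearing potential with male partners, who must "agree to practice two effective methods of birth control while receiving study drugs (as outlined in the subject information and consent form or" other subject documents.

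**Exemptions from testing.** The Pregnancy Test text in 5.3.1.1 says "Pregnancy tests are not required for female subjects with documented prior bilateral tubal ligation, bilateral oophorectomy or hysterectomy", and adds women confirmed postmenopausal. Table 7 footnote j lists the same four groups. So does Table 8 note c, which covers urine tests only. None of the three mentions a partner's vasectomy.

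**Testing rules.** In 5.3.1.1 the testing bullets stand under the line "For females of childbearing potential". One of them reads "Subjects that receive a RBV containing regimen will have pregnancy tests performed monthly throughout the Treatment Period and for a minimum of 7 months" after ribavirin stops, or as the local label or guidelines direct. Table 7 footnote j likewise ties the monthly post-ribavirin urine tests to women of childbearing potential.

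**Who gets ribavirin.** Under 5.1.2, subjects with GT1a infection and all GT1 subjects with compensated cirrhosis.

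**The concern.** Postmenopausal and surgically sterile status are properties of the woman. A partner's vasectomy is not: she remains fertile, the vasectomy can fail, and partners can change over treatment plus 7 months. The definition nevertheless puts her with women who cannot conceive, while the exemption lists treat her as someone to be tested. The term that the definition controls is the one that triggers the monthly ribavirin tests.

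The protocol's own rationale for criterion 2 is that ribavirin is a known teratogen. Under 5.4.1 and 6.6, ribavirin is stopped on a positive test or when the woman reports a pregnancy. With fewer tests, detection during treatment depends more on her own report, and a pregnancy could be exposed to ribavirin for longer before anyone acts.

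**Working it through.** The plan states no figure on this point, so there is none to reproduce. The check is a comparison of texts followed by a simple schedule calculation.

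**1. Routes to the label against the exemptions**

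| Status | Criterion 2: not of childbearing potential | Table 7 fn j | 5.3.1.1 | Table 8 note c (urine) |
|---|---|---|---|---|
| Postmenopausal | yes | exempt | exempt | exempt |
| Tubal ligation | yes | exempt | exempt | exempt |
| Oophorectomy | yes | exempt | exempt | exempt |
| Hysterectomy | yes | exempt | exempt | exempt |
| Vasectomized partner | yes | not named | not named | not named |

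Five statuses lead to the label and each list exempts four of them. The same one is absent every time. For the other four, definition and lists agree.

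**2. Which tests depend on the label**

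The monthly ribavirin tests depend on it through footnote j and the line above the bullets in 5.3.1.1. The tests at scheduled visits also appear in Table 7 itself, where footnote j excuses only the four groups. A site could therefore plausibly keep the visit tests and drop only the monthly tests that fall between visits.

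**3. Size of the gap if that happens**

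Assumptions:
- Monthly means every 4 weeks.
- Seven months = 7 × 30.44 days = 213 days = 30.4 weeks, giving seven four-weekly tests (post-treatment Weeks 4 to 28).
- The Table 7 urine tests fall at Day 1, Week 4, Week 12, end of treatment and the post-treatment visits. Those within 7 months are post-treatment Weeks 4, 12 and 24. The row is broken in extraction, so this is a reading of it.

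Longest gap between tests:

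| Period | Monthly tests kept | Visit tests only |
|---|---|---|
| On treatment, 12-week regimen | about 4 weeks | 12 − 4 = 8 weeks |
| On treatment, 24-week regimen | about 4 weeks | 24 − 12 = 12 weeks |
| Post-treatment, within 7 months | about 4 weeks | 24 − 12 = 12 weeks |

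Tests omitted per affected woman on ribavirin:
- 12-week regimen: Week 8 (1), plus post-treatment Weeks 8, 16, 20 and 28 (4) = 5.
- 24-week regimen: Weeks 8, 16 and 20 (3), plus the same 4 = 7.

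The documents do not say how many enrolled women would have a vasectomized partner, so no trial-level count can be given.

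**The case against.** The strongest reply is that the testing rules already settle the matter. Three texts written specifically about testing say who is exempt, they agree, and a partner's vasectomy is in none of them. Criterion 2 is an eligibility rule and says nothing about pregnancy tests. Specific procedural text normally governs a procedure, so testing her is the natural reading, and under it nothing is lost. This stands, and it is the main reason the point is minor. What it does not remove is that the monthly ribavirin requirement uses a term whose only definition in the protocol excludes her.

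A reader might infer more: that a site could omit every test. The screening rule "A serum pregnancy test will be performed at the Screening Visit only and sent to the central laboratory for analysis" and the Table 7 rule that begins "Pregnancy testing will be performed as specified in" also sit under the line about females of childbearing potential. The documents do not support that reading. The sentence naming who needs no test comes directly before that line, so in context the line means women not just exempted. Footnote j, which applies throughout the trial, and note c also leave her among the women to be tested.

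Nor can one say that nothing resolves the conflict. The exemption lists go most of the way. Criterion 2 defers birth-control detail to the consent form, and 5.3.1.1 allows the local ribavirin label or guidelines to set the post-ribavirin schedule; neither source is available here.

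Other safeguards remain. Section 5.2.3.2 asks subjects to use two contraceptive methods and 6.6 asks them to avoid pregnancy, in neither case with an exception for vasectomy. A reported pregnancy stops ribavirin without a scheduled test. The risk per woman is small, though not zero.

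**Conclusion.** The inconsistency is real and minor. Criterion 2 takes a fertile woman out of the group to which the monthly ribavirin tests apply, while the sponsor's own exemption lists leave her in. Most sites would test her. A site that applies the definition could drop the between-visit monthly tests, lengthening the longest interval from about 4 weeks to about 8 or 12 weeks on treatment and up to about 12 weeks afterwards. Those intervals rest on the reading of Table 7 and the four-weekly month set out above, and are illustrative.

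The longer intervals concern women given ribavirin. Women on DAAs only can carry the same label and have their own urine tests through post-treatment Week 4, so the definition should be corrected for them as well. Endpoints, sample size and analysis are not affected.

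**What to change.** In criterion 2 of 5.2.1 and in its Synopsis copy, take the vasectomized-partner clause out of the definition of not of childbearing potential. Make it a separate eligibility route, as is already done for women with female partners only. State there that these women, on ribavirin or on DAAs only, follow the pregnancy-testing schedule for females of childbearing potential. The three exemption lists need no change. The sponsor may also wish to say whether a partner's vasectomy counts as one of the two methods asked for in 5.2.3.2.

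The cost is a wording change to carry in an amendment, with the usual IEC/IRB approval and regulatory approval where required (Protocol 9.1). At a site that already follows the exemption lists it adds no tests. At a site that had dropped the monthly tests it adds roughly 5 to 7 urine tests per affected woman on ribavirin. Section 5.3.1.1 allows urine tests between visits to be done at home.

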### **Rationale for Inclusion Criteria**

(1, 4, 5) To select the appropriate subject population with sufficient disease severity for evaluation.

(2, 3,) RBV has known teratogenic effects. The impact of AbbVie DAAs on pregnancies is unknown.

(6) In accordance with harmonized Good Clinical Practice (GCP).

## 5.2.2 Exclusion Criteria

1. Women who are pregnant or breastfeeding.
2. Positive test result for Hepatitis B surface antigen (HbsAg) or confirmed positive anti-HIV antibody (HIV Ab) (test).
3. Use of medications listed below, or medications contraindicated for ritonavir or RBV (for those that receive RBV), within 2 weeks or 10 half-lives whichever is longer, prior to study drug administration including but not limited to:

**Table 6. Medications Contraindicated for Use with the Study Drug Regimen**

For medications contraindicated with AbbVie's 3 DAA regimen, refer to the recommended prescribing information section of the approved local product labels in countries where the regimen contained in this study (i.e., ABT-450/r/ABT-267 and ABT-333) has received marketing authorization. If locally approved labels are not available, refer to the following Contraindicated Medication list:

Alfuzosin	Ethinyl estradiol-containing medications	Pimozide
Astemizole	Fusidic Acid	Rifampin
Carbamazepine	Gemfibrozil	Salmeterol
Cisparide	Lovastatin	Sildenafil*
Dihydroergotamine	Methylergonovine	Simvastatin
Efavirenz	Midazolam (oral)	St. John's Wort
Ergotamine	Phenobarbital	Terfenadine
Ergonovine	Phenytoin	Triazolam

\* When used for the treatment of pulmonary arterial hypertension.

Note: Not all medications contraindicated with ritonavir, ribavirin, and 3DAA regimen are listed above. Refer to the most current package inserts or product labeling of ritonavir and ribavirin for a complete list of contraindicated medications.

4. Use of known moderate or strong inducers of cytochrome P450 3A (CYP3A) or strong inducers of cytochrome P450 2C8 (CYP2C8) or strong inhibitors of CYP2C8 within 2 weeks of the respective medication/supplement, prior to initial dose of study drug.
5. Clinically significant abnormalities or co-morbidities, other than HCV infection that in the opinion of the investigator make the subject an unsuitable candidate for this study or drug regimen.
6. Current enrollment in another interventional clinical study, previous enrollment in this study, prior or current use of any investigational or commercially available anti-HCV agents other than IFNs or RBV (including previous exposure to ABT-450, ABT-267 or ABT-333), or receipt of any investigational product within 6 weeks prior to study drug administration.
7. History of solid organ transplant.
8. Screening laboratory analyses showing any of the following abnormal laboratory results:
  - Creatinine Clearance (CrCl) < 30 mL/min as estimated by the Cockcroft-Gault equation:
$$\text{CrCl} = \frac{[(140 - \text{Age}) \times \text{Mass (in kg)} \times (0.85 \text{ if female})]}{[72 \times \text{Serum creatinine (in mg/dL)}]}$$
  - Albumin < 2.8 g/dL
  - Hemoglobin < LLN
  - Platelets < 25,000 cells per mm^3
  - Total bilirubin > 3.0 mg/dL
9. Any current or past clinical evidence of Child-Pugh B or C Classification (Child-Pugh Score  $\geq$  7) or clinical history of liver decompensation such as ascites (e.g., as noted on a physical exam or imaging test), variceal bleeding or hepatic encephalopathy.

10. Confirmed presence of hepatocellular carcinoma indicated on imaging techniques such as computed tomography (CT) scan or magnetic resonance imaging (MRI) within 3 months prior to Screening or on an ultrasound performed at Screening (a positive ultrasound result will be confirmed with CT scan or MRI.)
11. HCV genotype performed during screening indicating infection with any genotype other than genotype 1.

